3.3.1.7 Wound Healing and Surgery

VEGFR inhibitors can cause wound healing complications and wound dehiscence which may occur even long after a wound has been considered healed. Therefore, surgical and traumatic wounds must have completely healed before starting cabozantinib treatment and be monitored for wound dehiscence or wound infection while the subject is being treated with cabozantinib. If possible, cabozantinib treatment should be stopped for at least 28 days prior to major surgery.

3.3.1.8 Hypertension

Hypertension is a common class effect of drugs that inhibit VEGF pathways and has been reported among subjects treated with cabozantinib.

Blood pressure should be monitored in a constant position at each visit (either sitting or supine). Treatment guidelines for hypertension deemed related to cabozantinib are presented in Table 3-7. In general, subjects with known hypertension should be optimally managed before study entry. Decisions to decrease or hold the dose of study treatment must be based on blood pressure readings taken by a medical professional and must be confirmed with a second measurement at least 5 minutes after the first measurement. Other than for hypertension requiring immediate therapy, the presence of new or worsened hypertension should be confirmed at a second visit before taking therapeutic action. It is recommended that this second visit occurs within 1 week.

Table 3-7: Management of Hypertension Related to Cabozantinib

Criteria for Dose Modifications	Treatment/cabozantinib Dose Modification
Subjects not receiving optimized anti-hy	ypertensive therapy
> 150 mm Hg (systolic) and < 160 mm Hg or > 100 mm Hg (diastolic) and < 110 mm Hg	 Increase antihypertension therapy (ie, increase dose of existing medications and/or add new antihypertensive medications); Maintain dose of cabozantinib; If optimal antihypertensive therapy (usually to include 3 agents) does not result in blood pressure < 140 systolic or < 90 diastolic, or if the subject is symptomatic, the dose of cabozantinib should be interrupted and/or reduced.
≥ 160 mm Hg (systolic) and < 180 mm Hg or ≥ 110 mm Hg (diastolic) and < 120 mm Hg	 Interrupt and/or reduce cabozantinib by one dose level; Increase antihypertension therapy (ie, increase dose of existing medications and/or add new antihypertensive medications); Monitor subject closely for hypotension; If optimal antihypertensive therapy (usually to include 3 agents) does not result in blood pressure < 150 systolic or < 100 diastolic, dose of cabozantinib should be reduced further.
≥ 180 mm Hg (systolic) or ≥ 120 mm Hg (diastolic)	 Interrupt treatment with cabozantinib Add new or additional anti-hypertensive medications and/or increase dose of existing medications; Monitor subject closely for hypotension; When SBP < 150 and DBP < 100, restart cabozantinib treatment at one dose level lower; If optimal antihypertensive therapy (usually to include 3 agents) does not result in blood pressure < 150 systolic or < 100 diastolic, dose of cabozantinib should be reduced further.
Hypertensive crisis or hypertensive encephalopathy	Discontinue all study treatment

BP, blood pressure, SBP systolic blood pressure, DBP diastolic blood pressure

NOTE: If SBP and DBP meet different criteria in table, manage per higher dose-modification criteria

3.3.1.9 Thromboembolic Events

Thromboembolic complications are frequent in cancer patients due to procoagulant changes induced by the malignancy or anticancer therapy including inhibitors of VEGF pathways. Deep vein thrombosis and PE have been observed in clinical studies with

cabozantinib; including fatal events (please refer to the Investigator's Brochure). Subjects who develop a PE or DVT should have cabozantinib treatment held until therapeutic anticoagulation with heparins (eg, low molecular weight heparin [LMWH]) is established. (Note: Therapeutic anticoagulation with oral anticoagulants, eg, warfarin, or oral platelet inhibitors such as clopidogrel is not allowed in this study). Cabozantinib treatment may be resumed in subjects who are stable and have uncomplicated PE or DVT and are deriving clinical benefit from cabozantinib treatment. During anticoagulation treatment, subjects need to be monitored on an ongoing basis for bleeding risk and signs of bleeding which may require additional or more frequent laboratory tests in accordance to institutional guidelines. If there are any signs of clinically significant bleedings, cabozantinib treatment should be permanently discontinued.

Arterial thrombotic events (eg, transient ischemic attack, myocardial infarction) have been observed in studies with cabozantinib. Subjects should be evaluated for preexisting risk factors for arterial thrombotic events such as diabetes mellitus, hyperlipidemia, hypertension, coronary artery disease, history of tobacco use, and cardiac or thromboembolic events that occurred before initiation of study treatment. Cabozantinib treatment should be discontinued in subjects who develop an acute myocardial infarction or any other clinically relevant arterial thromboembolic complication.

3.3.1.10 Proteinuria

Proteinuria is an anticipated AE with the inhibition of VEGF pathways and has been observed in cabozantinib clinical studies, and nephrotic syndrome has been reported with cabozantinib and other inhibitors of VEGF pathways. Management guidelines are provided in Table 3-8.

Table 3-8: Management of Treatment-emergent Proteinuria

Severity of Proteinuria (UPCR)	Action To Be Taken
≤ 1 mg/mg (≤ 113.1 mg/mmol)	No change in cabozantinib treatment or monitoring.
> 1 and < 3.5 mg/mg (> 113.1 and < 395.9 mg/mmol)	 No change in cabozantinib treatment required; Consider confirming with a 24-hour protein assessment within 7 days; Repeat UPCR within 7 days and once per week. If UPCR < 1 on 2 consecutive readings, UPCR monitoring can revert to protocol-specific times. (Second reading is confirmatory and can be done within 1 week of first reading).
≥ 3.5 mg/mg (≥ 395.9 mg/mmol)	 Hold cabozantinib treatment pending repeat UPCR within 7 days and/or 24-hour urine protein; If ≥ 3.5 on repeat UPCR, continue to hold cabozantinib treatment and check UPCR every 7 days. If UPCR decreases to < 2, restart cabozantinib treatment at a reduced dose and monitoring of urine protein/creatinine should continue weekly until the UPCR decreases to < 1.
Nephrotic syndrome	Discontinue cabozantinib treatment.

UPCR, urine protein to creatinine ratio.

3.3.1.11 Corrected QTc Prolongation

The effect of orally administered cabozantinib at 140 mg/day (free-base equivalent) on QTc interval was evaluated in a randomized, double-blinded, placebo-controlled phase 3 study in patients with medullary thyroid carcinoma. A mean increase in QTcF of 10 - 15 ms was observed at 4 weeks after initiating cabozantinib. A concentration-QTc relationship could not be definitively established. Changes in cardiac wave form morphology or new rhythms were not observed. Accordingly, subjects in this study will be monitored for potential QT effects.

Other factors which may contribute to QTc prolongation include:

 Treatment with other drugs associated with QTc prolongation (see http://www.qtdrugs.org);

- Treatment with CyP 3A4 inhibitors (which may increase cabozantinib drug levels);
- Electrolyte changes (hypokalemia, hypocalcemia, hypomagnesemia);
- Medical conditions which can alter electrolyte status eg, severe or prolonged diarrhea.

Subjects having any of these additional risk factors while on cabozantinib must have electrocardiograms (ECGs) performed approximately one week after the onset of these factors.

If at any time on study there is an increase in QTc to an absolute value > 500 msec, two additional ECGs should be performed within 30 minutes after the initial ECG with intervals not less than 3 minutes apart. If the average QTc calculated by the Friderica formula (QTcF) from the three ECGs is > 500 msec, study treatment must be withheld and the following actions should be taken:

- Check electrolytes, especially potassium, magnesium and calcium. Correct abnormalities as clinically indicated;
- If possible, discontinue any QTc-prolonging concomitant medications;
- Repeat ECG triplets hourly until the average QTcF is ≤ 500 msec or otherwise determined by consultation with a cardiologist.

The MD Anderson Cancer Center/IND Office should be notified immediately of any QTc prolongation event:

• Subjects with QTc prolongation and symptoms must be monitored closely until the QTc elevation has resolved. Cardiology consultation is recommended for evaluation and subject management. Symptomatic subjects must be treated in accordance with standard clinical practice. No additional study treatment is to be given to the subject until after the event has resolved, the subject has been thoroughly evaluated, and further treatment has been agreed to by the MD Anderson Cancer Center/IND Office. If any additional study treatment is given (eg, after correction of electrolyte abnormalities and normalization of QTcF), it will be at a reduced dose as agreed to by the investigator and the MD Anderson Cancer Center/IND Office.

3.3.1.12 Hypophosphatemia

Hypophosphatemia has been reported during treatment with cabozantinib. Serum phosphorus should be monitored frequently while receiving cabozantinib. Mild hypophosphatemia is usually asymptomatic or symptoms can be non-specific such as weakness, bone pain, rhabdomyolysis, or altered mental status. Other causes of hypophosphatemia such as poor nutrition, chronic alcoholism, malabsorption, excessive antacid use, glucocorticoids use, kidney dysfunction, respiratory alkalosis, vitamin D deficiency should be ruled out and/or these causes treated in accordance to standard of care. Mild to moderate hypophosphatemia should be managed by oral replacement including food that are high in phosphate (diary items, meats, beans) and/or oral phosphate supplements in accordance to standard clinical practice guidelines.

Clinically relevant hypophosphatemia should be managed in accordance to the dose modification guidelines as outlined in Table 3-2 and Table 3-3 or as clinically indicated.

3.3.1.13 Thyroid Function Disorders

Changes in thyroid function tests (TFTs) and hypothyroidism have been reported with cabozantinib and other tyrosine kinase inhibitor treatment as a result of altered thyroid hormone regulation by mechanisms that seem to be specific for each agent (Torino et al. 2009). Preliminary data from ongoing studies indicate that treatment-emergent elevation of thyroid stimulating hormone (TSH) by cabozantinib may be dose-dependent in fashion. Hyperthyroidism has also been reported. Currently available data are insufficient to determine the mechanism of TFT alterations and its clinical relevance. Routine monitoring of thyroid function and assessments for signs and symptoms associated with thyroid dysfunction is recommended before initiation and during treatment with cabozantinib. Management of thyroid dysfunction (eg, symptomatic hypothyroidism) should follow accepted clinical practice guidelines and dose modification guidelines as outlined in Table 3-2³².

3.3.1.14 Hemorrhagic Events

Hemorrhagic events have been reported with approved drugs that inhibit VEGF pathways as well as with cabozantinib. In order to mitigate risk of severe hemorrhage, subjects should be evaluated for potential bleeding risk factors before initiating cabozantinib treatment and monitored for bleeding events with serial complete blood counts and physical examination while on study. Risk factors for hemorrhagic events may include (but may not be limited to) the following:

- Tumor of the lung with cavitary lesions or tumor lesions which invades, encases, or abuts major blood vessels. The anatomic location and characteristics of tumor as well as the medical history must be carefully reviewed in the selection of subjects for treatment with cabozantinib;
- Recent or concurrent radiation to the thoracic cavity;
- Active peptic ulcer disease, ulcerative colitis, and other inflammatory GI diseases;
- Underlying medical conditions which affect normal hemostasis (eg, deficiencies in clotting factors and/or platelet function, or thrombocytopenia);
- Concomitant medication with anticoagulants or other drugs which affect normal hemostasis;
- History of clinically significant hemoptysis.

Discontinue cabozantinib treatment in subjects who have been diagnosed with a severe bleeding complication.

3.3.1.15 GI Perforation/Fistula and Non-GI Fistula Formation

GI perforation/fistula and non-GI fistula formation have been reported with approved drugs that inhibit VEGF pathways as well as with cabozantinib. Carefully monitor for episodes of abdominal pain, especially among subjects with known risk factors for developing GI perforation/fistula, and carefully monitor subjects with known risk factors for non-GI fistula, to allow for early diagnosis. Such risk factors include (but may not be limited to) the following:

GI perforation/fistula:

- Intra-abdominal tumor/metastases invading GI mucosa;
- Active peptic ulcer disease, inflammatory bowel disease, diverticulitis, cholecystitis or symptomatic cholangitis, or appendicitis;
- History of abdominal fistula, GI perforation, bowel obstruction, or intraabdominal abscess;
- Prior GI surgery (particularly when associated with delayed or incomplete healing). Complete healing after abdominal surgery or resolution of

intra-abdominal abscess must be confirmed before initiating treatment with cabozantinib.

Additional risk factors include concurrent chronic use of steroid treatment or nonsteroidal anti-inflammatory drugs. Constipation indicative of bowel obstruction should be monitored and effectively managed.

Non-GI fistula:

Complications from radiation therapy has been identified as a possible predisposing risk factor for non-GI fistula formation among subjects undergoing treatment with VEGF pathway inhibitors (eg, bevacizumab).

Discontinue cabozantinib treatment in subjects who have been diagnosed with GI or non-GI perforation/fistula.

3.3.1.16 Osteonecrosis of the Jaw

Osteonecrosis of the jaw (ONJ) has been reported with use of anti-angiogenic drugs and bisphosphonates and denosumab in cancer patients. Additional risk factors for ONJ have been identified such as use of corticosteroids, chemotherapy, local radiotherapy, poor oral hygiene, smoking, dental or orofacial surgery procedures, and cancer disease itself. Osteonecrosis has been reported among subjects treated with cabozantinib, the details of which are provided in the current version of Investigator's Brochure. As a preventive measure, invasive dental procedures should be avoided if possible in subjects who have previously been treated with or concomitantly receive bisphosphonates or denosumab.

In cases where dental procedures are unavoidable, the risks and benefits of a dental procedure and the extent of the procedure as well as the risk of developing ONJ need to be considered when deciding on the duration of a temporary treatment interruption of cabozantinib. If clinically possible, treatment with cabozantinib should be held for approximately 4 weeks before a dental procedure and resumed after complete healing has occurred.

Subjects with any documented case of osteonecrosis should have study treatment interrupted, and appropriate clinical management should be initiated. Reinitiation of study treatment must be discussed with and approved by the MD Anderson Cancer Center/IND Office on a case-by-case basis.

3.4 Concomitant Medications and Therapies

3.4.1 Anticancer Therapy

Local intervention is discouraged unless medically unavoidable. Subjects receiving local intervention (eg, palliative radiation) are allowed to continue to receive study treatment at the investigator's discretion.

3.4.2 Other Medications

All concomitant medications used by the subject (including prescription and over-the-counter medications, transfusions, vitamins, herbal remedies, and nutritional supplements) during the period from 28 days before the first dose of study treatment through 30 days after the date of the decision to permanently discontinue study treatment are to be recorded in the case report forms.

3.4.3 Allowed Therapies

- Antiemetics and antidiarrheal medications are allowed prophylactically in accordance to standard clinical practice if clinically indicated;
- Granulocyte colony-stimulating factors (G-CSF or GM-CSF) are allowed if used per clinical guidelines (eg, American Society of Clinical Oncology [ASCO] or [European Society for Medical Oncology] ESMO guidelines);
- Drugs used to control bone loss (eg, bisphosphonates and denosumab) are allowed if started before screening activities and may be initiated or exchanged during the course of the study as clinically indicated, at PI discretion;
- Transfusions, hormone replacement, and short term higher doses of corticosteroids should be utilized as indicated by standard clinical;
- Individualized anticoagulation therapy with heparin is allowed if it can be provided safely and effectively under the following circumstances:
 - Low dose heparins for prophylactic use are allowed if clinically indicated and the benefit outweighs the risk per the investigator's discretion;
 - o Therapeutic doses of LMWH after the first dose of study treatment are allowed if clinically indicated (eg, for the treatment of deep venous thrombosis), and the benefit outweighs the risk per the investigator's discretion. For

management of thromboembolic complications while on study, refer to section 3.3.1.9.

- Accepted clinical guidelines regarding appropriate management while receiving anticoagulation therapy with heparins must be followed. This includes, but is not limited to, subject education regarding potential adverse drug reactions, monitoring laboratory parameters, dose adjustments (eg, due to kidney dysfunction);
- o For restrictions on oral anticoagulants see Section 3.4.4.
- Antacids, H₂ blockers, or proton-pump inhibitors should be taken at least 2 hours (preferably 4 hours) after taking cabozantinib and at least 14 hours before the next dose of cabozantinib, if possible.

Potential drug interactions with cabozantinib are summarized in Section 3.4.5.

3.4.4 Prohibited or Restricted Therapies

The following therapies are prohibited while the subject is on study:

- Any investigational agent or investigational medical device;
- Any drug or herbal product used specifically for the treatment of malignant PH and PG;
- Therapeutic doses of oral anticoagulants (eg, warfarin or other coumarin-related agents, direct thrombin or direct FXa inhibitors, or antiplatelet agents such as clopidogrel, or chronic use of aspirin above low dose levels for cardioprotection per local applicable guidelines);
- Any other systemic anticancer treatment (eg, chemotherapy, immunotherapy, radionuclides) and local anticancer treatment such as surgery, ablation, or embolization.

The following therapies should be avoided if possible, while the subject is on study:

•

- Erythropoietic stimulating agents (eg, epoetin alfa and darbepoetin alfa) should not be used based on a report of increased risk of tumor recurrence and/or progression associated with erythropoietin (Wright 2007);
- Chronic co-administration of cabozantinib with strong inducers of the CYP3A4
 family (eg, dexamethasone, phenytoin, carbamazepine, rifampin, rifabutin,
 rifapentine, phenobarbital, and St. John's Wort) may significantly decrease
 cabozantinib concentrations and should be avoided. Selection of alternate
 concomitant medications with no or minimal CYP3A4 enzyme induction
 potential is recommended;
- Caution must be used when discontinuing treatment with a strong CYP3A4 inducer in a subject who has been concurrently receiving a stable dose of cabozantinib, because this could significantly increase the exposure to cabozantinib;
- Co-administration of cabozantinib with strong inhibitors of the CYP3A4 family (eg, ketoconazole, itraconazole, clarithromycin, indinavir, nefazodone, nelfinavir, and ritonavir) may increase cabozantinib concentrations and should be avoided.
 Grapefruit and Seville oranges may also increase plasma concentrations of cabozantinib and should be avoided.

Additional information on potential drug interactions with cabozantinib is provided in Section 3.4.5.

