1 BACKGROUND AND RATIONALE

1.1 Background:

Pheochromocytomas (PHs) and paragangliomas (PGs) are rare neuroendocrine tumors originating in the paraganglia. Approximately 15-20% of these tumors are malignant¹. Patients with metastatic disease exhibit a decreased overall survival, with only 60% of patients still living five years after initial diagnosis². Malignant PHs and PGs have two characteristics: increased angiogenesis³ and predilection for bone metastases⁴.

Tumor angiogenesis

Approximately 50% of patients with malignant PHs and PGs carry germline mutations of the succinate dehydrogenase subunit B (SDHB) gene. These mutations prevent oxidative catabolism of succinate into fumarate and electron transport through the internal mitochondrial membrane. As a consequence, production of ATP is attenuated leading to activation of hypoxia-inducible target genes such as vascular endothelial growth factors (VEGFs) and the platelet-derived growth factor beta (PDGF-β). In addition, genes involved in glucose metabolism such as the hexokinase 2 (HK2) and lactate dehydrogenase (LDH) are also up-regulated⁵. Activation of these genes causes abnormal and increased tumor angiogenesis, decreased apoptosis, and increased glucose uptake. In fact, 18F-FDG-PET/CT scan offers 100% sensitivity for the localization of these tumors⁶. Some sporadic tumors exhibit a similar molecular profile⁵.

Bone metastases

The skeleton is involved in 80% of patients with malignant PHs and PGs4. In 20% of these patients, the skeleton is the only location of metastatic spread⁴. Bone metastases are usually lytic and blastic, expansile, and associated with increased morbidity and decreased overall survival⁴. Up to eighty percent of patients with bone metastases develop skeletal related events (SREs) such as: bone pain, fractures, and cord compression that need radiation therapy and/or surgery⁴. Patients experience SREs rapidly once bone metastases are developed (median 4.4 months)⁴. Fifty percent of patients who develop an SRE develop a second SRE within a median of 10 months⁴. Palliative radiation therapy and surgery are frequently required to improve pain and release cord compression. Molecular targeted therapies and chemotherapy may prevent SREs⁴.

Experience with molecular targeted therapies

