2.5 Withdrawals

Subjects may discontinue study treatment or withdraw their consent to participate in the study at any time without prejudice. The investigator may withdraw a subject from study treatment or from the study if, in his or her clinical judgment, it is in the best interest of the subject or if the subject cannot comply with the protocol.

In addition, any of the following conditions require discontinuation of the subject from study treatment:

- An AE or intercurrent illness that in the opinion of the investigator warrants the subject's withdrawal from study treatment;
- Specific conditions described in the Management of Adverse Events Sections 3.3.1 and 3.3.1.3;
- Necessity for treatment with other anticancer treatment prohibited by protocol;
- Sexually active subjects who refuse to use medically accepted barrier methods of contraception (eg, male condom, female condom) during the course of the study and for 4 months after discontinuation of study treatment;
- Women who become pregnant or are breastfeeding;
- If the subject does not recover from his or her toxicities to tolerable Grade ≤ 2 within 6 weeks, the subject will have study treatment discontinued unless there is unequivocal evidence that the subject is benefitting. In this situation, a subject may be able to restart therapy with a dose reduction upon resolution of the toxicity;

- Request by regulatory agencies for termination of treatment of an individual subject or all subjects under the protocol;
- Significant noncompliance with the protocol schedule in the opinion of the investigator;
- The minimum dose of study treatment will be 20 mg once daily (qd). Subjects who cannot tolerate 20 mg qd will have study treatment discontinued;
- Progressive disease (PD) as determined by the investigator unless the patient is deriving clinical benefit as judged by the investigator (case-by-case decision with approval of the Medical Monitor).

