3.3 Cabozantinib Dose Modifications, Interruptions, and Discontinuation

Subjects will be monitored for AEs from the time of signing informed consent through 30 days after the date of the decision to permanently discontinue cabozantinib treatment. Subjects will be instructed to notify their physician immediately at the onset of any AE. Causality assessment of AEs should include at minimum confounding factors such as

disease and concomitant medications. AE severity will be graded by the investigator in accordance with CTCAE v.4.0.

The following should be taken into consideration in decisions regarding dose modifications (reductions or interruption):

- As a general approach all AEs should be managed with supportive care at the earliest signs of toxicity considered related to the study treatment. Should this be ineffective, dose interruptions and/or reductions should be considered to prevent worsening of toxicity.
- Dose modification criteria for cabozantinib are detailed in Section 3.3. Dose interruptions and/or reductions should be implemented for unacceptable toxicity. Doses may be modified at any time while on study.
- The assigned dose for cabozantinib is 60 mg/day. 20 mg dose reduction levels of cabozantinib are permitted (see Table 3-2).
- Dose reductions or interruptions may also occur in the setting of lower grade toxicity than defined in Sections 3.3.1 and 3.3.1.3, if the investigator feels it is in the interest of a subject's safety and will optimize drug tolerability.
- Interruption of cabozantinib treatment for AEs may occur at any time per investigator discretion. If treatment is interrupted due to AEs for more than 6 weeks, cabozantinib should be discontinued unless there is unequivocal evidence that the subject is benefitting. In this situation, a subject may be able to restart therapy with a dose reduction upon resolution of the toxicity.
- Dose interruptions for reason(s) other than AEs (eg, surgical procedures) can be longer than 6 weeks per the discretion of the investigator.

Guidelines for the management of specific AEs are provided in Section 3.3.1.3.

Table 3-2: Dose Reductions of Cabozantinib

Assigned dose	First Dose Level Reduction	Second Dose Level Reduction
60-mg cabozantinib oral qd	40-mg cabozantinib oral qd	20-mg cabozantinib oral qd

qd= once daily

Cabozantinib should be discontinued if a qd dose of 20-mg cabozantinib (minimum dose) is not tolerated

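### Sections 3.4.1 and 3.4.4, the latter enforced by Section 2.5, give opposite consequences for study treatment when a patient needs tumor surgery, ablation or embolization

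*Combined protocol and SAP*

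**What the plan says.** Three sections bear on what happens when a patient needs local treatment during the study.

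- Section 3.4.1 (Anticancer Therapy): "Local intervention is discouraged unless medically unavoidable". It goes on: "Subjects receiving local intervention (eg, palliative radiation) are allowed to continue to receive study treatment at the investigator's discretion".
- Section 3.4.4 (Prohibited or Restricted Therapies) opens its first list with "The following therapies are prohibited while the subject is on study". The last item on that list, after systemic anticancer treatment, is "local anticancer treatment such as surgery, ablation, or embolization". No exception is given for unavoidable cases, and Section 3.4.1 is not mentioned.
- Section 2.5 (Withdrawals) states that "any of the following conditions require discontinuation of the subject from study treatment". One of those conditions is "Necessity for treatment with other anticancer treatment prohibited by protocol".

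The background (Section 1.1) describes skeletal related events as including "fractures, and cord compression that need radiation therapy and/or surgery". Section 2.1 makes time to such events, and their incidence at 4 months and one year, exploratory endpoints in the bone-only branch. One-year PFS is a secondary endpoint for all patients.

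**The concern.** A stopping rule should give one answer for one event. Here two sections answer differently, and the investigator must pick. The trial is open-label, single-arm and run at one site, so the person choosing knows how the patient is doing.

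The choice matters beyond drug exposure. Protocol-scheduled imaging stops when treatment stops, so the reading chosen also decides whether the patient goes on being assessed for progression. Treatment that may include surgery is foreseeable in this disease, and the events that prompt it are counted as endpoints in the bone-only branch. The situation is therefore expected, not remote.

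**Working it through.** The documents give no figure on this point, so the check is mainly textual.

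**Step 1. Compare the trigger.** Under Section 3.4.1, medical necessity is what makes a local intervention acceptable and compatible with continuing. Under Section 2.5, read with Section 3.4.4, necessity is what requires stopping. Section 2.5 adds no separate conflict. It gives the Section 3.4.4 prohibition its consequence. Other items in the same Section 2.5 list carry exceptions (unresolved toxicity with evidence of benefit; progression with clinical benefit), but this item carries none.

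**Step 2. Go through the procedures one by one.**

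| Procedure | Section 3.4.1 | Sections 3.4.4 and 2.5 | Result |
|---|---|---|---|
| Tumor surgery, ablation or embolization that cannot be avoided | A local intervention; may continue if the investigator agrees | Named as prohibited; needing it requires discontinuation | Opposite consequences |
| Palliative radiation | Named as the example; may continue | Not named, but the list is open-ended | Can be read consistently as allowed; the boundary is not stated |
| Surgery for a fracture or cord compression | A local intervention on an ordinary reading | Prohibited only if it counts as anticancer, which is not defined | Undetermined |

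Both lists work by example (*eg* in one, *such as* in the other), so neither closes off the other's territory.

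**Step 3. Trace the effect on data.** Table 5-1 has no tumor assessment, bone scan or FDG-PET/CT entry in the post-treatment column. Section 5.3 describes one return visit 30 to 37 days after the last dose, with laboratory and physical examinations. A patient who continues is imaged every 8 weeks to week 52; a patient who is stopped has no further scheduled imaging. Section 7 names Kaplan-Meier estimation but gives no rule for PFS after a local intervention or after treatment stops without progression.

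**Step 4. Weight of one patient.** With about 22 patients, one patient is 1/22 = 4.5 percentage points of a simple one-year proportion, ignoring censoring. This gives the scale per patient; it does not estimate how many are affected.

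**Step 5. Check that the primary design figures are untouched.** The plan's intervals follow p ± 1.96 × √(p(1 − p)/n) at p = 0.45:

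- n = 14: 1.96 × √(0.45 × 0.55/14) = 0.261, giving 18.9% to 71.1%.
- n = 8: 1.96 × √(0.45 × 0.55/8) = 0.345, giving 10.5% to 79.5%.

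Both match the protocol. They depend only on p and n, so the conflict does not enter them.

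**The case against.** The best defence is that the sections divide the ground between them: palliative radiation under Section 3.4.1, all other local anticancer treatment under Section 3.4.4. For radiation this largely succeeds. It is expressly compatible with continuing and is absent from the prohibited local list. A reader might infer that every local therapy, radiation included, is caught in a contradiction; the text does not support that. The defence does not rescue surgery, ablation and embolization, because Section 3.4.1 speaks of local intervention in general and is not limited to radiation.

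Three further inferences are tempting and should not be drawn.

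- *That decompression for cord compression is clearly a mandatory stop.* Section 1.1 describes such surgery as palliative, and Section 3.4.4 prohibits anticancer treatment. The documents do not say on which side it falls, so this is an ambiguity and not a settled prohibition.
- *That Section 3.3 is a further contradiction.* It says "Dose interruptions for reason(s) other than AEs (eg, surgical procedures) can be longer than 6 weeks per the discretion of the investigator". This need not refer to anticancer surgery; Sections 3.3.1.7 and 3.3.1.16 show that general surgery and dental procedures are also foreseen.
- *That about 12 of 22 patients are affected.* The route would be: half of main-branch patients have bone metastases (40/(40 + 40) from Section 1.3), so 0.5 × 14 = 7; 7 + 8 = 15; 0.80 × 15 = 12. But the 80% is an upper figure for all skeletal events, including bone pain and cases treated by radiation alone, and it has no time horizon. The 4.4-month median runs from the development of bone metastases, not from enrolment. The share treated surgically is not given. The inputs also disagree: Section 1.1 puts skeletal involvement at 80%, while Section 1.3 implies 40% + 20% = 60%.

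It can fairly be added that imaging ends after any discontinuation, not only this kind. That is true, and it is a separate matter. What belongs here is that contradictory text leaves open who is discontinued. With a single arm at one site, no between-arm or between-site bias arises.

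**Conclusion.** The point holds for surgery, ablation and embolization: an unavoidable procedure permits continuation under Section 3.4.1 and requires discontinuation under Sections 3.4.4 and 2.5, and both cannot be followed. For palliative radiation a consistent reading exists but depends on inference. For surgery after a fracture or cord compression the governing rule is undetermined.

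What is exposed is time on treatment and the completeness of follow-up for one-year PFS. The size of any shift cannot be derived, because the documents do not give the number of on-study patients who would need one of these procedures. The conclusion rests on an ordinary reading of local intervention as covering the procedures that Section 3.4.4 names, and on Table 5-1 and Section 5.3 being the full imaging schedule. It should be corrected, but it does not threaten the primary analysis. No view is taken on which clinical rule is right.

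**What to change.** Reconcile Sections 3.4.1, 3.4.4 and 2.5 so that each type of local intervention has one stated consequence for study treatment, chosen by the sponsor. The types to cover are palliative radiation, surgery for a skeletal event, other tumor surgery, ablation and embolization. Add cross-references so that the three sections point to the same rule. Record the date, site and reason of each local intervention on the CRF.

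The cost is amendment wording and one CRF field, with no extra patients. Continuing tumor imaging after discontinuation would add procedures and is not part of this change.
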